Following BCG vaccination, it is expected that nearly all individuals will exhibit a positive tuberculin skin test (also referred to as a purified protein derivative test or PPD) for a period of approximately five to seven years. Thus, latent TB testing via PPD method may be confounded by BCG vaccination. However, latent TB status can still be accurately determined by diagnostics blood tests (ex: QuantiFERON-TB Gold and ELISPOT TB).

Common adverse events from intradermal BCG vaccination include pain at injection site, a local skin reaction at the site of vaccination, which may ulcerate and scar, cause regional suppurative lymphadenitis, and osteitis, a rare complication (approx. complication rate

0.39/1,000,000). The most serious complication of BCG vaccination is disseminated BCG infection. The most frequent disseminated infection is BCG osteomyelitis (0.01 to 43 cases per 1,000,000 doses). Fatal disseminated BCG infection has occurred at a rate of 0.06-1.56 cases/1,000,000 doses. These primarily have occurred in immunocompromised hosts who are excluded from participating in this study.

There are rare case reports that vaccination against other viral infections, including SARS-Co-V2 and influenza, can cause transient erythema at the site of previous BCG vaccination, with no longterm clinical consequences.

Rarely, BCG vaccination can lead to transient vaccine-induced lymphadenopathy, which may present diagnostic dilemma for women undergoing screening mammography for breast cancer.

Common adverse events from routine blood draws include mild pain at blood draw site, minor bleeding and/or bruising.

b. Steps taken to minimize the risks.

Experienced nursing and research staff from the JH CIR will perform the intradermal vaccinations and study blood draws.

To minimize concerns, we are excluding individuals with immunosuppression, children, elderly, and pregnant/breastfeeding participants.

To minimize confounding results on mammography, female participants will be advised to delay screening mammography performed for a minimum of 3 months following BCG vaccination.

We will adhere to guidance on DSMB activities (see attachment). The data and safety monitoring plan will include reporting any adverse events to the IRB and the DSMB in the quarterly progress reports. In addition, we have a detailed plan on how to deal with serious adverse events that may arise, which will include reporting to the chair of the DSMB and IRB within 24-hours of notification. The study will be conducted according to the FDA's Good Clinical Practice Guidelines.

A DSMB has been created to function as an independent group of experts who will advise the study investigators. The members of the DSMB will serve in an individual capacity and provide their expertise and recommendations. The members are not co-investigators of the study and have no undisclosed conflict of interest.

Safety Monitoring Plan:

Following BCG administration, participants will be instructed to contact the investigative team if she or he experiences symptoms such as fever of 101.5°F or greater, or acute localized inflammation persisting longer than 2-3 days, which would be suggestive of active infections. If an illness of this degree has occurred, an evaluation for a serious infectious complication will be performed which includes consultation with an infectious disease physician. In individuals who develop persistent fever or experience an acute febrile illness consistent with BCG infection,

two or more antimycobacterial agents will be administered while diagnostic evaluation, including mycobacterial blood cultures are conducted.

The DSMB will also be charged with reviewing any complaints from patients, family members, and clinicians about any aspect of the study including recruitment procedures and study implementation. All potential participants will be provided with contact information to register complaints, if they experience adverse events, coercion or other problems. Participant complaints will be reported to the IRB pursuant to Hopkins policies. The DSMB will modify or stop the study if any such complaints represent a legitimate concern about the study procedures or methods.

The DSMB has the authority to halt the study if it perceives that harm is occurring due to the intervention.

c. Plan for reporting unanticipated problems or study deviations:

All unanticipated problems or study deviations will be reported per standard Johns Hopkins IRB procedures.

d. Legal risks such as the risks that would be associated with breach of confidentiality.

The data are being recorded on an encrypted laptop and SAFE Desktop. All files will be password protected. Only specified study team members will have access to the data. The data set will not include any sensitive information. All blood samples will be deidentified and will not be traceable back to participant.

e. Financial risks to the participants. N/A

9. Benefits

- a. Description of the probable benefits for the participant and for society.
 - Individual benefits: The individual may experience positive emotions from contributing to the development of patient-centered interventions by being able to share their experiences. They may also benefit from the protective nature of the BCG vaccine.
 - Societal benefits: This study will provide formative information regarding the efficacy of the BCG vaccine to provide immunity towards NTM infections. These data will inform future larger studies designed to study regarding the efficacy of the BCG vaccine against NTM infections in the CF and NCFB populations.

10. Payment and Remuneration

- a. Detail compensation for participants including possible total compensation, proposed bonus, and any proposed reductions or penalties for not completing the protocol.
 - Healthy controls will be compensated \$80 for completion of the screening visit if they are found to be eligible and enrolled in the study.
 - Study participants from all arms will receive \$200 for the initial visit where they will undergo a blood draw and be administered the BCG vaccine. Participants will then receive \$80 for each subsequent study blood draw. Total compensation for participation in this study will be \$360 (excluding compensation for screening of healthy controls).

11. Costs

- a. Detail costs of study procedure(s) or drug (s) or substance(s) to participants and identify who will pay for them.
 - There will be no costs directed towards the participants.

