For participants in the CF arm, the CFQR respiratory questionnaire will be completed by the study participant and turned in to the study team. For participants in the NCFB arm, the QOL-B and the MRC dyspnea score will be completed by the study participant and turned in to the study team. (See **Appendix B** - **Schedule of study surveys/standardized instruments**; Validated PRO instruments provided in **Supplemental Study Documents**).

Pregnancy testing/counseling regarding pregnancy:

For women of childbearing potential, a urine pregnancy test will be performed. Only individuals with a negative pregnancy test will be allowed to continue in the study. Pregnancy prevention counseling will be provided to recommend the avoidance of becoming pregnant in the first month following vaccination.

Research phlebotomy:

Approximately 75cc of blood will be drawn for baseline, pre-vaccination analysis (see Appendix A schedule of sample collection).

BCG reconstitution:

The BCG (TICE® strain; purchased from Merck) will be reconstituted by the Johns Hopkins Investigational Drug Pharmacy under a biosafety cabinet under BSL-2 conditions. BCG (TICE® strain) will be prepared using aseptic technique by adding 1mL of sterile water to one vaccine vial (contains 1×10^8 CFU). For the purposes of this study, reconstituted BCG will be further diluted in sterile water, such that each 0.1mL of the BCG TICE® will contain an estimated 2 x 10^6 CFU of *M. bovis* BCG).

Intradermal BCG vaccination:

A trained research nurse from the JH CIR will perform the vaccination procedure **per study site Standard Operating Procedure (SOP) for intradermal vaccination.** Briefly a sterile syringe containing 0.1mL of the BCG TICE® with 2 x 10⁶ CFU of *M. bovis* BCG will be injected intradermally into the deltoid region of the arm.

Symptom diary instruction:

The participant will be instructed to keep a post-vaccination diary of symptoms (see Symptom Diary in supplemental documents). The diary will be completed once weekly for the first month post-vaccination. The diary will be turned in to the study team at the one-month post-vaccination study visit.

Safety monitoring phone call (day 2):

Virtual safety monitoring:

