e. Justification of why participants will not receive routine care or will have current therapy stopped.

N/A. All CF and NCFB participants will continue to receive routine standard care for bronchiectasis without any interruptions.

f. Justification for inclusion of a placebo or non-treatment group.

All participants will receive the intradermal BCG vaccination. There is no placebo or nontreatment group in this study. Following the results of this study, a larger, blinded, placebocontrolled trial may be designed. g. Definition of treatment failure or participant removal criteria.

The goal of this study is not to achieve efficacy in prevention of infections, but rather to assess biomarkers of immune protection that are altered by BCG vaccination of vulnerable populations. Study samples will not be analyzed in real time.

Given these factors, we do not have specific criteria for participant removal. If there are unforeseen circumstances during which a participant will not be able to present for study visits 2 and 3 (research phlebotomy visits), these will be evaluated on a case by case basis by the PI.

h. Description of what happens to participants receiving therapy when study ends or if a participant's participation in the study ends prematurely.

This is a single vaccine design and there is no further booster vaccine planned. Participants will continue to receive standard of care for their medical conditions during and after study completion.

5. Inclusion/Exclusion Criteria

• Inclusion criteria (CF/NCFB arms):

- Confirmed diagnosis of either CF or NCFB
- Adult male and non pregnant females ages 18-65 (inclusive)
- \circ FEV1 \geq 40%
- Willingness to participate in the study after all aspects of the protocol have been explained and written informed consent obtained.
- o Available for the study duration, including all planned follow-up visits

• Inclusion criteria (healthy controls):

- Adult male and non pregnant females ages 18-65 (inclusive)
- Negative HIV enzyme-linked immunosorbent assay (ELISA), rapid antibody test and/or confirmatory test, if necessary, at screening
- Willingness to participate in the study after all aspects of the protocol have been explained and written informed obtained
- Available for the study duration, including all planned follow-up visits

• Exclusion criteria (all arms):

- Current or prior history of active or latent TB (per report, not formally tested) or NTM infection
- Prior BCG vaccination

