- Previous vaccine in the past 4 weeks
- History of severe anaphylaxis to any vaccine or vaccine components
- History of organ/bone marrow transplantation or other immunosuppressing condition, including HIV
- Immunosuppressing drugs (including oral corticosteroids equivalent to >10mg of prednisone for 5 days) in the 30 days prior to study enrollment
- o Cirrhosis or portal hypertension
- Pregnant or breastfeeding

- Receipt of another investigational product in the last 28 days or planned receipt during this study
- Has any other condition that, in the opinion of the principal investigator, would preclude informed consent, make study participation unsafe, complicate interpretation of study outcome data, or otherwise interfere with achieving study objectives

6. Drugs/ Substances/ Devices

a. The rationale for choosing the drug and dose or for choosing the device to be used.

The BCG vaccine is given intradermally to infants and children worldwide to protect against disseminated TB in most countries except the US and Canada. Its dosing for intradermal vaccination and safety profile is well established.

We have specifically chosen the BGC vaccine to test its effects on NTM because the BCG vaccine has been shown to provide some protection against diseases other than TB by boosting the immune system through trained immunity. Furthermore, based on a recent study by Abate et al there is evidence that the BCG increases protective immunity against NTM in healthy subjects¹⁶.

Due to a current global shortage of BCG VACCINE TICE®, we have received approval from the FDA to use TICE® BCG labeled for intravesical use in this study. These products are identical in formulation, but are labeled differently to indicate different routes of administration.

For this study, the selected dose of BCG TICE® is 0.1mL (~1x10⁶ CFU), which is lower than the package insert dose of (0.2-0.3 mL of 2-3 x10⁷ CFU). The lower dose was chosen to be consistent with the BCG dose used in a recent study by Abate et al. that showed the BCG (TICE® strain) induced blood-based markers of protection against NTM in healthy controls¹⁶.

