In addition, we are using intradermal administration instead of the percutaneous administration that is approved by the FDA. Intradermal route has been chosen for two reasons: 1) in comparison to percutaneous administration, intradermal administration provides more standard person-to-person dosing, and 2) intradermal dosing has been shown to provide a more robust immune response compared to percutaneous administration²⁴.

b. Justification and safety information if FDA approved drugs will be administered for non-FDA approved indications or if doses or routes of administration or participant populations are changed.

TICE® BCG for intravesical use is licensed by the FDA in the US and is indicated for the treatment and prophylaxis of carcinoma in situ (CIS) of the urinary bladder, and for the prophylaxis of primary or recurrent stage Ta and/or T1 papillary tumors²².

BCG VACCINE TICE® for percutaneous use is licensed by the FDA in the U.S. for the prevention of tuberculosis in persons not previously infected with *M. tuberculosis* who are at high risk for exposure. The Advisory Committee on Immunization Practices (ACIP) and the Advisory Committee for the Elimination of Tuberculosis recommends the BCG intradermal vaccine for the following circumstances²³:

- 1. Infants and children with negative tuberculin skin tests who are (a) at high risk of intimate and prolonged exposure to persistently untreated or ineffectively treated patients with infectious pulmonary TB (b) continuously exposed to persons with infectious pulmonary tuberculosis who have bacilli resistant to isoniazid and rifampin, and the child cannot be separated from the presence of the infectious patient.
- 2. TB exposed health care workers in high risk settings where (a) a high percentage of TB patients are infected with *M. tuberculosis* strains that are resistant to both isoniazid and rifampin, (b) transmission of such drug resistant *M. tuberculosis* strains to health care workers and subsequent infection is likely (c) comprehensive TB infection control precautions have been implemented, but have not been successful.

Our study does not include any of these indications. The purpose of this study is to evaluate whether BCG vaccine can be effective in protection against NTM infections in patients with CF and NCFB. We have received an IND exemption from the FDA for the use of BCG in this study (See supplemental study documents).

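### The protocol gives two doses for the same 0.1 mL BCG injection: 2 x 10^6 CFU in section 4a and about 1 x 10^6 CFU in section 6a

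*Combined protocol and SAP*

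**What the plan says.** Section 4a (BCG reconstitution) has the Investigational Drug Pharmacy add 1 mL of sterile water to a vial holding 1 x 10^8 CFU. Then "reconstituted BCG will be further diluted in sterile water" so that "each 0.1mL of the BCG TICE® will contain an estimated 2 x 10^6 CFU". The next paragraph (Intradermal BCG vaccination) describes the injection as "a sterile syringe containing 0.1mL of the BCG TICE® with 2 x 10⁶ CFU". Neither paragraph gives a dilution factor or a diluent volume.

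Section 6a (rationale for drug and dose) says "the selected dose of BCG TICE® is 0.1mL (~1x10⁶ CFU"). It sets this figure against the labelled dose and puts it below that dose: "which is lower than the package insert dose of (0.2-0.3 mL of 2-3 x10⁷ CFU"). The reason it gives is: "The lower dose was chosen to be consistent with the BCG dose used in a recent study". That study, in healthy volunteers, is cited, but its CFU dose is not reported in the protocol.

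Section 4f confirms that there is no untreated arm: "All participants will receive the intradermal BCG vaccination". Section 6b adds: "We have received an IND exemption from the FDA for the use of BCG in this study". The exemption itself is in supplemental documents that are not part of the public file.

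**The concern.** All three dose statements describe the same product, the same 0.1 mL volume and the same single vaccination. Two say 2 x 10^6 CFU and one says about 1 x 10^6 CFU. Either section 4a tells staff to give twice the dose that section 6a presents, or section 6a misreports the dose.

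This matters because BCG is the only intervention. It is a live vaccine planned for 60 people in each of three arms (180 in all), two of them patient arms with CF or NCFB. The use already departs from the labelling: the stock is labelled for intravesical use, the dose is below the insert dose, and the route is intradermal where the approved one is percutaneous. Section 6a is where a reader learns what dose was chosen and why, and its figure is half of the one in the working instructions. The immune-response results also need one correct dose if they are to be reproduced or carried into the larger placebo-controlled trial that the protocol foresees.

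**Working it through.** **Inputs**

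- Vial: 1 x 10^8 CFU in 1 mL after reconstitution (section 4a).
- Injection volume: 0.1 mL (sections 4a and 6a).
- Target dose: 2 x 10^6 CFU (section 4a, twice); about 1 x 10^6 CFU (section 6a, once).
- Package-insert dose as quoted in section 6a: 2-3 x 10^7 CFU in 0.2-0.3 mL.

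**Step 1. Are the two sections on the same scale?** The insert figure can be reproduced from the vial strength:

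- 0.2 mL x 1 x 10^8 CFU/mL = 2 x 10^7 CFU
- 0.3 mL x 1 x 10^8 CFU/mL = 3 x 10^7 CFU

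This matches section 6a, so both sections use the same units and the same vial strength. The gap is not a difference of convention.

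**Step 2. What dilution does each figure need?** Undiluted, 0.1 mL holds 0.1 x 1 x 10^8 = 1 x 10^7 CFU. The fold dilution is 1 x 10^7 divided by the target dose. The final volumes assume that the whole 1 mL is diluted.

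| | Section 4a | Section 6a |
|---|---|---|
| Dose in 0.1 mL | 2 x 10^6 CFU | 1 x 10^6 CFU |
| Concentration (dose / 0.1 mL) | 2 x 10^7 CFU/mL | 1 x 10^7 CFU/mL |
| Fold dilution | 1 x 10^7 / 2 x 10^6 = 5 | 1 x 10^7 / 1 x 10^6 = 10 |
| Final volume from 1 mL | 5 mL (add 4 mL) | 10 mL (add 9 mL) |
| Times below insert dose, lower end | 2 x 10^7 / 2 x 10^6 = 10 | 2 x 10^7 / 1 x 10^6 = 20 |
| Times below insert dose, upper end | 3 x 10^7 / 2 x 10^6 = 15 | 3 x 10^7 / 1 x 10^6 = 30 |

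The ratio of the stated doses is 2 x 10^6 / 1 x 10^6 = 2.

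**Step 3. Can the text settle it?**

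- *Approximation.* Live counts vary from vial to vial, so the hedged wording in both sections is fair for a realised count. These are nominal targets, though, and they call for two different preparations.
- *A misread character.* The 2 x 10^6 figure appears twice in section 4a in two typographic forms, and the digit that differs is the leading one, not an exponent.
- *Superseded text.* The document has no amendment log that marks either figure as replaced.
- *The dilution instruction.* None is given, so in the protocol as published the target CFU alone fixes the dilution, and the target CFU is the number in conflict.
- *The rationale.* Both figures are below the insert dose. The other reason, agreement with the earlier study, cannot be tested without that study's dose.

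**The case against.** The mismatch itself is hard to dispute, so the case on the other side is about how much it matters.

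The only text that tells anyone what to prepare or inject is in section 4a, and its two statements agree. Staff who follow the procedures meet one figure, while section 6a is narrative and hedges its number. The statement that the dose is below the package insert holds for both figures by at least ten-fold, so no stated justification is shown to fail at 2 x 10^6 CFU. Nothing in the documents shows that risk differs between the two doses; immunosuppressed people are excluded, and a DSMB and stopping rules are in place. Pharmacy or FDA files outside the public document may already fix the dilution. Volumes such as 4 mL or 9 mL also presume that the whole vial is diluted in one step.

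Much of this stands. The documents do not show that anyone received a different dose or was exposed to added risk, and the diluent volumes illustrate the arithmetic and nothing more. It does not remove the conflict. The section that presents and defends the dose gives a different number from the section that orders it. The margin below the insert dose is also limited reassurance, because it compares an approved percutaneous dose with an intradermal one. That both figures fit the same argument means only that the argument cannot tell them apart.

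**Conclusion.** The concern holds. The protocol states the dose of its only intervention in two ways that differ by a factor of two, which corresponds to 1:5 against 1:10 dilution of the reconstituted vial, and at least one statement is wrong as written. The arithmetic rests only on the vial strength and volumes in section 4a and the insert dose quoted in section 6a.

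The consequences are limited. The stated power does not depend on the CFU figure, and a common dose of either size would not by itself bias the contrast between patients and controls. This is an inconsistency in the description of the treatment, not a flaw in the analysis. It still has to be corrected, because it concerns a live vaccine used outside its labelling and given to every participant. The documents do not allow a judgement on which figure is right.

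**What to change.** 1. Confirm the intended dose against the Investigational Drug Pharmacy's preparation instructions and the submission behind the FDA IND exemption.
2. State one CFU figure in both sections 4a and 6a.
3. In section 4a, give the dilution explicitly: 1:5 for 2 x 10^6 CFU per 0.1 mL, or 1:10 for 1 x 10^6 CFU. If the whole 1 mL is diluted in one step, that means adding 4 mL or 9 mL of sterile water.
4. Check that the claimed agreement with the earlier healthy-volunteer study holds for the confirmed figure, and reword section 6a if it does not.
5. If vaccination has begun, report the dose actually prepared.

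The cost is a record check and a few lines of protocol text, with no added participants, visits or procedures.
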